Outcomes will be pre - post quantified validated measures of gambling behaviour, anxiety and depression; feasibility and acceptability: ability to recruit people who are sports betting and acceptability of the intervention i.e., number of sessions attended and use of mobile phone and video conferencing to provide therapy. Pre and post outcome data will support existing evidence from our own and others trials to confirm the effect sizes and sample size for a larger phase 2 randomised controlled trial

Phase 2:

Use the learnings and effect size change in the CET group from phase 1 to implement a randomised controlled trial and recruit 140 people who provide consent and baseline data and test the efficacy of the experimental intervention (CET) versus control intervention.

Rationale / justification - How the research will fill any gaps and/or contribute to the field of research or contribute to existing or improved practice?

There are no proven treatments for sports betting internationally. This studies phase 1 and 2 would be the first beyond a case series that would demonstrate pre-post outcome measures to test a highly accessible psychological treatment for sports betting gambling disorder.

Research project setting - i.e. Where is the research being conducted i.e. FMC, GP Plus Marion, Noarlunga Hospital, Tonsley building, Sturt Campus, online forums and alternatives

Please ensure you list the site plus clinic/department / service.

The study will be based at The Flats – Flinders Psychological Therapy Services FMC site from where the therapists will deliver CET and usual care by phone or internet remotely to either SA or whole of Australia. Recruitment will occur for individuals across the whole of SA for phase 1 and all Australia for phase 2.

Methodological approach - clearly describe the specific procedures or techniques that will be used to answer the research question and meet the aims.

The intervention: in the published 6 cases treated by SGTS CET was provided face to face by experienced SGTS staff using a standardised workbook adapted for sports betting. The graded exposure-based approach identifies triggers which elicit a gambling urge and the person then systematically using homework tasks, grades their approach to each trigger until habituation of the gambling urge occurs. Ultimately all urges to gamble are extinguished and the person gains control over their gambling either through abstinence or occasional gambling.

Pilot trial phase 1 (SA)

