How will the study data be destroyed?

The study data will be securely erased from the secure archive repository under the management of the Flinders University, Information and Digital Services (IDS) department

Matching and sampling strategies:

Phase 1: We will aim to recruit 40 people with a sports betting addiction for the pilot study. Based on our case studies and the literature, the majority (80-90%) will be young males. As all participants will be offered the intervention there will be no need to match or stratify.

Phase 2: We aim to randomise 140 people with sports betting addiction equally to 2 groups. Some will have sports betting alone, others will have other forms of gambling. We will stratify based on sports betting alone and sports betting plus other forms of gambling.

A biostatistician will independently generate random sequences for each stratum using Stata version 11.1 software and delivered these to the Flinders clinical trials call centre of a centrally located hospital pharmacy. RAs, collecting and entering data and therapists administering interventions will not know in advance which treatment the next participant would receive.

Accounting for potential bias, confounding factors and missing information:

In phase 2 consecutive recruitment of larger sample (140) from anywhere in Australia where someone has access to the internet including rural and remote areas should minimize bias. Eligible individuals will be randomly assigned to 1 of 2 treatment groups with 1:1 allocation ratio before their pre-treatment assessment with a therapist. From the trial outset, randomisation will be blocked to increase the likelihood of equal group sizes, using a standard permuted block algorithm in which block sizes were randomly chosen from 2, 4, and 6 to protect concealment.

In this trial, therapists will know what treatment they are administering and participants will be provided with information that rationalises and describes their assigned therapy protocol. It is intended that participants are masked to the study hypothesis in order to help limit the likelihood for self-report bias. Participant information sheet will refer to treatments as “well known and commonly used psychological treatments”. To avoid contamination of masking, SGTS administration staff members will be instructed not to reveal specific treatment labels to any participants and therapists not to reveal the alternative treatment label.

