Fidelity: All therapy sessions will be audio recorded and in phase 1 all sessions will be listened to by CIs [name], [name] and [name] and rated using the adapted 10 item checklist which was developed based on the Cognitive Therapy Scale (CTS) which is an 11-item instrument with good reliability when used by experienced clinicians (Young & Beck, 1980), used for a previous SGTS study of CET vs Cognitive Therapy. ([name] et al). In phase 2, 20% of sessions will be randomly selected from early, mid, and late study phases and checked for therapy fidelity.

Baseline differences will be corrected for if required and missing data will be handled by multiple imputation

Sample size and statistical or power issues – Make sure the size and profile of the sample to be recruited is adequate to answer the research question – please provide details:

Phase 2: In our sample size calculations, we assume a correlation between follow-up measures of r 0.7 (Frison & Pocock, 1992). Based on a type I error rate of 5%, power of 90%, two-tailed test, and a VGS standard deviation of 10.2 units ([name] et al., 2010), to detect a significant difference of 8% (i.e. 4.8 points on the scale) in mean VGS scores between the CET and control groups, 50 participants were required in each group. Given the treatment drop-out rate experienced in

the SGTS treatment programme (approximately 35%) we therefore needed to recruit 70 participants in each group of the study giving a total sample size of 140 participants.

How will you measure, manipulate and/or analyse the information collected?

Phase 1 and 2: The primary analysis will use all available data and follow an intent-to-treat principle to investigate any statistically significant differences in primary and secondary outcomes over time between both groups. Secondary analyses will be conducted based on 'as treated' and 'per protocol' approaches within a counterfactual framework using inverse probability weighting (IPW) (Hernan & Hernandez-Diaz, 2012). The IPW uses the inverse of the probability of being in the observed treatment group.

Generalised mixed-effects models will be used in the analysis of repeated measures for primary and secondary continuous and categorical outcomes. Fixed effects (time-invariant variables) in models were intervention group, time in continuous form (intervention period and follow-up), and interaction between group and time.

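### The Phase 2 drop-out allowance does not follow from its own inputs: keeping 50 per arm after 35% loss needs 77 per arm, and 70 leaves about 45

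*Protocol*

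**What the plan says.** The calculation is in the protocol section on sample size and statistical or power issues, and concerns Phase 2 only. Its inputs are:

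- Error rates: "Based on a type I error rate of 5%, power of 90%, two-tailed test".
- Variability: "a VGS standard deviation of 10.2 units".
- Target difference: "a significant difference of 8% (i.e. 4.8 points on the scale".
- Correlation: "we assume a correlation between follow-up measures of r 0.7".
- Result before drop-out: "50 participants were required in each group".
- Allowance for the service's treatment drop-out rate: "approximately 35%) we therefore needed to recruit 70 participants in each group of the study giving a total sample size of 140 participants".

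Allocation is equal; the section on bias, confounding and missing information has participants "randomly assigned to 1 of 2 treatment groups with 1:1 allocation ratio". The total of 140 recurs elsewhere, for example under expected outcomes, where the aim is to "recruit 140 people who provide consent and baseline data". No section gives another allowance or a rounding rule that would explain 70.

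Two other statements bear on what the 35% means. The analysis section plans a primary intent-to-treat analysis using all available data, and missing data are to be multiply imputed. The answer on participant withdrawal says that data already recorded will be kept but not used in the study.

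**The concern.** An allowance for loss has to divide the required number by the proportion retained. Here 50 is raised to 70, an increase of 40%, while 35% loss calls for an increase of about 54% (1/0.65 = 1.54). The stated requirement, loss rate and recruitment target therefore cannot all hold. Anyone who takes the paragraph at its word will believe that 35% loss still leaves the 50 per arm needed for 90% power, and it does not. What is at stake is the accuracy of the power claim for the planned randomised trial. The pilot's target of 40 is not affected.

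**Working it through.** **Inputs** (all from the sample-size section): difference 4.8 points (8% of the 0-60 scale: 0.08 x 60 = 4.8), SD 10.2, r = 0.7, two-sided 5%, power 90%, 50 per arm before loss, loss 35%, 70 per arm after. Allocation is 1:1.

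**Step 1: reproduce the 50.** The protocol names no formula. For two means, n per arm = 2(z₀.₉₇₅ + z₀.₉₀)² SD²/d².

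- Unadjusted: 2 x (1.960 + 1.2816)² x 10.2²/4.8² = 94.9.
- Adjusted for one baseline, with one follow-up: multiply by 1 - r² = 1 - 0.49 = 0.51, giving 48.4, or 49 after rounding up.

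The stated 50 agrees with the second line. Other uses of r = 0.7 do not give 50:

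| Basis | n per arm |
|---|---|
| No adjustment, one follow-up | 95 |
| Change from baseline, one follow-up | 57 |
| Mean of 2 or 3 follow-ups, no baseline | 81 or 76 |
| Baseline-adjusted, 2 or 3 follow-ups | 35 or 30 |
| Change from baseline, 2 or 3 follow-ups | 43 or 38 |

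The baseline-adjusted, single follow-up basis is used below.

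**Step 2: the allowance for loss.**

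- Required: 50/(1 - 0.35) = 76.9, so 77 per arm and 154 in total. The stated total is 154 - 140 = 14 short, or 14/154 = 9%.
- Starting from the unrounded-up 49 does not rescue it: 49/0.65 = 75.4, so 76 per arm.
- Retained from 70: 70 x 0.65 = 45.5 per arm.
- Loss at which 70 still keeps 50: 1 - 50/70 = 28.6%.
- For comparison, 50 x 1.35 = 67.5. The 70 may have come from multiplying by 1.35 and rounding up, but that is a guess at its origin.

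**Step 3: effect on power.** The adjusted SD is 10.2 x √0.51 = 7.284. The standard error of the difference is 7.284 x √(2/n), and power is approximately Φ(4.8/SE - 1.960).

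- n = 50: SE = 1.457, 4.8/SE = 3.295, power = Φ(1.335) = 90.9% (90.4% with the noncentral t).
- n = 45.5: SE = 1.527, 4.8/SE = 3.143, power = Φ(1.183) = 88.2% (87.5% with the noncentral t).
- Difference detectable with 90% power at 45.5 per arm: 3.2416 x 1.527 = 4.95 points, against 4.8.

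**Step 4: sensitivity to the loss rate**, because the protocol gives it as approximate (70 recruited per arm, normal approximation):

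| Loss | Retained per arm | Power |
|---|---|---|
| 30% | 49.0 | 90.3% |
| 32.5% | 47.25 | 89.3% |
| 35% | 45.5 | 88.2% |

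**The case against.** The strongest reply is that the 35% is a rate of leaving treatment, not of missing outcomes. The primary analysis is intent-to-treat on all available data. Willingness to give follow-up data is an inclusion criterion, and in Phase 2 the research assistant, not the therapist, does the follow-up at 3 and 12 months. In the Phase 1 design, the 35% expected to have no or minimal therapy (5 + 10 + 20) are kept as a comparison group, so their outcomes are evidently expected. If all 70 per arm gave outcomes, nominal power would be about 97%, before any dilution of the effect by untreated time. This stands as a limit on the conclusion. It does not repair the paragraph, which inflates for these people as though they were lost. The rule that a withdrawing participant's recorded data are not used also means that some real loss is to be expected.

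A second reply is that an approximate 35% absorbs the gap. It does so only partly: at 30% loss power is still about 90%, but at the stated rate it is not.

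Three stronger readings are tempting and are not supported:

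- A reader might infer that the trial will not have 90% power. That holds only if those who leave treatment contribute no outcome data, and the protocol does not say so.
- A reader might compute power for change from baseline and arrive at about 82-83% at 45.5 per arm. That basis needs 57 per arm and so is not the one behind the 50. Power on it would already be about 86% with the full 50, so most of that fall comes from changing the analysis, not from the allowance.
- A reader might assume that 140 will pass unreviewed into the national trial. The expected-outcomes section says that pilot data will be used to confirm the effect sizes and sample size.

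**Conclusion.** The point holds as a minor arithmetic error in a stated sample-size figure. On the protocol's own inputs, 35% loss needs 77 per arm (154 in total), and 70 per arm retains about 45. Power for 4.8 points is then about 87-88% against the stated 90%, a shortfall of about 2 to 2.5 percentage points.

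The mismatch between 50, 35% and 70 rests on no assumption beyond the protocol's own wording. The size of the power loss rests on two: that the 50 came from a baseline-adjusted comparison at a single follow-up (the only basis tried that reproduces it), and that the 35% provide no outcome. If the second is wrong, the loss of power is smaller or absent. Neither the validity of the planned comparison nor the pilot is threatened.

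**What to change.** Keep 140 and restate the figure in the sample-size section, for example: *With 70 per arm and 35% of participants without outcome data, about 45 per arm are evaluable, giving about 87-88% power for a difference of 4.8 points; 50 per arm are retained if outcome loss is at most 28%.*

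In the same paragraph, say whether the 35% measures stopping therapy or missing outcome data, and give the assumed loss of outcome data as a separate figure with its basis. The 35% should not simply be relabelled as outcome loss: the protocol sources it as treatment drop-out and gives no outcome-loss rate.

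The cost is a change of wording, with a slightly less favourable power figure and no change to design or recruitment. If the sponsor prefers to keep 90% power at 35% outcome loss, the total becomes 154, which means 14 more participants and an edit wherever 140 appears.

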
Recruitment: 40 subjects to be recruited over a 3-month period in SA using social media, i.e., Facebook and Instagram to recruit on-line sports betting gamblers and through the OPG Gambling Help Services throughout SA.

Design: this would be a 12-month single arm trial with all participants being offered CET. Participants would receive up to 10 sessions (30-60 mins) provided over 2 months and follow up for another 3 months. We will recruit until we have 40 people who have provided signed consent forms and baseline questionnaires. All will be offered the intervention. As for all psychological interventions, of the 40, a proportion will not attend a single session (~5%), some will attend a single assessment only session (~10%) and others only 1 assessment and 1-2 therapy sessions (~20%) leaving about 65% who attend 4 or more sessions. (ie one assessment + 3 therapy sessions). This provides a naturalistic comparison group ie 35% of the sample who received no or minimal intervention compared to the intervention group (65%) who we will define as having 'an adequate dose' of the intervention. We will also conduct a per

protocol analysis of those who completed all 10 sessions to see the effect of the full dose of the intervention.

Phase 2:

140 subjects will be randomised to intervention (CET) or control ie usual care, in a 2-arm parallel 26 month randomised controlled trial, each arm receiving up to 10 sessions over 12 weeks delivered by phone and/or videoconferencing. Each participant will be followed for 12 months post intervention to determine outcomes of gambling behaviour, problem gambling severity, anxiety, depression and work and social adjustment.

Consumer and Community engagement – investigators are encouraged to consult with [Consumer and Community groups](#) with the design of their research. Please outline any consultation that has occurred.

SGTS has an active consumer group led by [name] a former client of SGTS who has recovered from a gambling addiction. He is employed 0.1FTE by SALHN to provide support to gamblers about to start treatment and during treatment. He has provided input to the design of the workbook and will be asked to continue his current role in contacting participants in the trial during their therapy to provide education and support as well as obtain feedback on the acceptability of the intervention.

What are your outcome measures?

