The RA will contact the person to arrange a suitable time to go through the trial information, providing the patient information and consent form (PICF) electronically. If the person gives consent, they may sign this form electronically and return it electronically or print and scan or

print and post the form. They will also be asked to complete the baseline questionnaires at this or a subsequent session. These are returned as above. Once the questionnaires are completed the RA will arrange for the trial therapist to contact the person to commence CET (phase 1).

For phase 2, at this point the RA will contact the Clinical Trials centre to obtain the randomisation allocation. They will then provide the appropriate therapist information to contact the person to commence the first therapy session.

Intervention: CET. The first session includes asking the person to put Money Management in place ie ceasing or pausing credit card/phone/efpost access, cancelling phone and internet gambling accounts, arranging for a daily or weekly allowance managed by a significant other. All participants are given a standardised treatment rationale during their first session and checked if they agree to proceed with the treatment plan. They are also helped to define a problem statement and end of treatment goal. They receive a standard mental health and CBT assessment screening for co-morbid psychiatric disorders and risk to self or others.

The CET treatment is delivered in individual sessions and conducted according to a detailed manual which is adapted from one used previously in a randomised control trial ([name] et al. 2015). Treatment comprises up to 10 weekly 30-60-min sessions, though participants may have receive fewer or a greater number of sessions depending on the pace at which they moved through their graded cue exposure hierarchy.

During the second session an initial hierarchy of gambling cues is developed which is altered according to the clients' insights and responses throughout

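### One treatment-group weight is stated for both the as-treated and the per-protocol analysis, which leaves the secondary per-protocol estimate open to selection on progress in therapy

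*Protocol*

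**What the plan says.** The analysis section of the Protocol (*How will you measure, manipulate and/or analyse the information collected?*) covers Phases 1 and 2 together. On the primary analysis it says: "The primary analysis will use all available data and follow an intent-to-treat principle". On the secondary analyses: "Secondary analyses will be conducted based on 'as treated' and 'per protocol' approaches within a counterfactual framework using inverse probability weighting (IPW". It then defines the weight in one sentence: "The IPW uses the inverse of the probability of being in the observed treatment group". It gives no separate weight for the per-protocol analysis, and it does not say what the observed treatment group is.

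Three other places bear on this:

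- *Accounting for potential bias, confounding factors and missing information* uses the term treatment groups for the randomised arms of Phase 2: "Eligible individuals will be randomly assigned to 1 of 2 treatment groups with 1:1 allocation ratio".
- The Phase 1 *Design* paragraph plans a per "protocol analysis of those who completed all 10 sessions to see the effect of the full dose of the intervention". It also contrasts an adequate-dose group (4 or more sessions, about 65%) with those who had no or minimal intervention (about 35%).
- *Intervention: CET* allows up to 10 sessions, but also "fewer or a greater number of sessions depending on the pace at which they moved through their graded cue exposure hierarchy".

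**The concern.** The two secondary analyses have different selection problems. An as-treated contrast must correct for which treatment a person received. A per-protocol contrast drops people who depart from protocol, so it must correct for who stays. A weight for treatment group is made for the first task. It does the second only if group is taken to mean the dose received and the weight model includes what drives departure.

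One likely driver is progress during therapy, because the CET description ties session number to it. Progress also predicts outcome. If it affects who stays more strongly in one arm than in the other, the per-protocol comparison sets two differently selected groups against each other while being presented as a counterfactual estimate. In Phase 1 the full-dose estimate is exposed to selection of the same kind.

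**Working it through.** **Inputs from the Protocol.** Allocation is 1:1. The VGS standard deviation is 10.2, the target difference 4.8 points and the correlation between follow-up measures 0.7. Treatment drop-out is about 35%, so about 65% stay.

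The point rests on no figure stated in the Protocol, but these inputs do reproduce the Phase 2 sample size. 2 × [10.2 × (1.960 + 1.282) / 4.8]² = 94.9 per group, and 94.9 × (1 − 0.7²) = 48.4, so 49 against the stated 50.

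**Step 1: the weight if the group is the assigned arm.** In Phase 2 every participant has probability 0.5, so the weight is 1/0.5 = 2. In Phase 1 there is one arm, so it is 1/1 = 1. A constant weight cancels from a weighted mean, so the per-protocol estimate is the unweighted one.

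**Step 2: the possible size of the bias under that reading.** The assumptions, none of them in the Protocol, are:

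- no true treatment effect;
- an early-therapy severity score E, standardised and normal;
- correlation 0.7 between E and the final VGS (the Protocol's value, applied to this pair);
- 65% adherence in each arm;
- log-odds of adherence changing by b per SD of E in the CET arm, and not at all in the control arm.

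With p(E) the probability of adhering, the mean of E among CET adherers is b × E[p(1 − p)] / 0.65. The bias in VGS points is that mean × 0.7 × 10.2.

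| b (logit per SD) | E[p(1 − p)] | mean of E among adherers | bias (SD) | bias (VGS points) |
|---|---|---|---|---|
| −1 | 0.190 | −0.292 | −0.205 | −2.1 |
| −0.5 | 0.216 | −0.166 | −0.116 | −1.2 |
| +0.5 | 0.216 | +0.166 | +0.116 | +1.2 |
| +1 | 0.190 | +0.292 | +0.205 | +2.1 |

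A negative b means that people doing well stay, which favours CET. A positive b means that they leave, which counts against it.

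**Step 3: what different weights do.** A separate simulation (400,000 participants per scenario, no true effect, 65% adherence) used a baseline score as well as an early score with SD about 1.1. Its early score is more strongly related to outcome, at 0.7 × 1.118 / 0.929 = 0.84, so its biases are larger than those in Step 2. The per-protocol difference in VGS points was:

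| Weight | CET only, responders stay | CET only, half the dependence | CET only, responders leave | Equal dependence in both arms |
|---|---|---|---|---|
| None | −2.56 | −1.46 | +2.53 | 0.06 |
| 1/P(arm) = 2 | −2.56 | −1.46 | +2.53 | 0.06 |
| 1/P(arm given baseline) | −2.56 | −1.47 | +2.53 | 0.07 |
| 1/P(adherent given arm, baseline) | −2.13 | −1.18 | +2.09 | 0.05 |
| 1/P(adherent given arm, baseline, early score) | −0.04 | 0.00 | 0.00 | 0.03 |

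An arm weight changes essentially nothing. An adherence weight on baseline alone removes a small part of the bias. Adding response during therapy removes nearly all of it, as it should when the model contains the true driver.

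**The case against.** The strongest reply is that the sentence says observed, not assigned, and applies to both phases. An assigned-arm weight would be pointless in a single-arm Phase 1, whereas the Phase 1 design supplies observed groups defined by dose. On that reading the weight does model who adheres. No covariate is excluded, and the covariates of a weight model are commonly left to the SAP, which is not shown. This stands, and it rules out saying that the weight cannot correct for adherence. It does not settle the matter. The Protocol uses treatment groups for the randomised arms elsewhere, and a single definition still serves two analyses that need different weights.

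A reader might also infer that the per-protocol estimate will be biased in favour of CET because responders are the ones retained. The Protocol does not support that direction. The pace rule allows fewer as well as more sessions, so fast progressors may finish early and those who complete all 10 could be the slower ones. Nor does a rule about pace show by itself that adherence depends on response, since it describes permitted variation.

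Two limits on the illustration also stand. In the Phase 1 design, 65% is the share expected to reach 4 or more sessions, so many of those who leave would have no session-4 score. The early score in the working therefore stands for whatever was recorded before departure. And near-complete removal of the bias is a best case: with about 0.65 × 70 = 45 adherers per arm, estimated weights will be noisier and the true driver may not be fully measured.

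**Conclusion.** The point holds as a defect in a stated weight. The Protocol gives one treatment-group weight for two analyses. Depending on the reading, that weight either does nothing for the per-protocol analysis or does an unspecified amount. The secondary per-protocol estimate is therefore left open to selection bias of unknown sign.

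Under the assumed settings of Step 2, the bias is about 1.2 to 2.1 VGS points either way, which is 25% to 43% of the 4.8-point target (1.18/4.8 and 2.09/4.8). It is close to zero if adherence depends on response equally in both arms. CET-only dependence is plausible, because the pace rule belongs to the exposure hierarchy and the control workbook sessions have no such rule, but the Protocol does not establish it. These two-arm figures do not quantify the Phase 1 estimate.

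A flat statement that the per-protocol result is confounded by early response, or any single figure for the bias, would go beyond the document. Only secondary analyses are affected, so this is a change that should be made rather than one on which the trial's main conclusion depends.

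**What to change.** - Define the observed treatment group (assigned arm, or treatment or dose received) for each phase, and keep that weight for the as-treated analysis only.
- For the per-protocol analysis, define departure from protocol. In doing so, reconcile the Phase 1 set of those completing all 10 sessions with the CET description, which permits fewer or more.
- Censor at departure, and weight by the stabilised inverse probability of remaining adherent. Model it by arm on baseline variables and the measures taken at each session (gambling time and money, PHQ-9, GAD-7), plus the session-4 questionnaires for those who reach session 4.

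The cost is a few sentences of plan and an adherence model on data that the Protocol already collects. The downside is more variable weights and a wider interval, which will be felt most in Phase 1 with 40 participants. The intention-to-treat primary analysis does not change.
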